# **16 AUDITING AND MONITORING**

The purpose of an audit or regulatory inspection is to verify the accuracy and reliability of clinical study data submitted to a regulatory authority in support of research or marketing applications, and to assess compliance with statutory requirements regulations governing the conduct of clinical studies.

In accordance with applicable regulations, GCP and Indivior procedures, the clinical monitor(s) will periodically contact the site, including conducting on-site visits at intervals agreed by the Investigator and documented in the Clinical Monitoring Plan and the Site Initiation Visit Report.

The clinical monitor(s) will contact the site prior to the start of the study to discuss the protocol and data collection procedures with site personnel. In accordance with applicable regulations and GCP guidelines, the Investigator shall make available for direct access all study-related records upon request by Indivior, Indivior's agents, clinical monitor(s), auditors and/or IRB. The monitors will visit the site during the study in addition to maintaining frequent telephone and written communication. The extent, nature, and frequency of on-site visits will be based on such considerations as the study objectives and/or endpoints, the purpose of the study, study design complexity and enrolment rate.

The Investigator must allow the clinical monitor(s) direct access to all relevant documents and to allocate his/her time and the time of his/her staff to the clinical monitor(s) to discuss findings and any relevant issues.

Upon completion of the study, study closeout activities must be conducted by Indivior or its designee in conjunction with the PI, as appropriate.

Steps to be taken to ensure the accuracy and reliability of data include the selection of qualified Investigators and appropriate study centers, review of protocol procedures with the Investigators and associated personnel before the study, periodic monitoring visits by Indivior, and direct transmission of clinical laboratory data from a central laboratory into Indivior's (or designee's) database. Written instructions will be provided for IMP preparation and dosing, collection, preparation and shipment of blood, plasma samples. Guidelines for CRF completion will be provided and reviewed with study personnel before the start of the study. Indivior (or designee) will review CRFs for accuracy and completeness during on-site monitoring visits and after transmission to Indivior (or designee). Any discrepancies will be resolved with the Investigator or suitably qualified designee, as appropriate.

This study will be organized, performed and reported in compliance with the protocol, SOPs, working practice documents and applicable regulations and guidelines.

In accordance with the standards defined in Indivior SOPs and applicable regulatory requirements, clinical studies sponsored by Indivior are subject to Indivior Quality Assurance (QA) Investigator Site Audits that may be delegated to a Contract Research Organization or Indivior contract auditors. Investigator Site Audits will include review of, but are not limited to, drug supply, presence of required documents, the informed consent process and comparison of

Confidential

CRFs with source documents. The Investigator agrees to participate with audits conducted at a reasonable time in a reasonable manner. Full consultation with the Investigator will be made prior to and during such an audit, which will be conducted according to Indivior's or a Contract Research Organization's QA SOPs. In addition, this study is subject to inspections by Regulatory Authorities. If such a regulatory inspection occurs, the Investigator agrees to allow the regulatory inspector direct access to all relevant study documents. The Investigator must contact Indivior immediately if this occurs and must fully cooperate with the inspection conducted at a reasonable time in a reasonable manner.

# **17 AMENDMENTS**

Protocol modifications, except those intended to reduce immediate risk to study subjects, may be made only by Indivior. A protocol change intended to eliminate an apparent immediate hazard to subjects may be implemented immediately, provided the IRB is notified within 5 days.

Any permanent change to the protocol must be handled as a protocol amendment. The written amendment must be submitted to the IRB and the Investigator must await approval before implementing the changes. Indivior or designated representative will submit protocol amendments to the appropriate Regulatory Authorities for approval.

If in the judgment of the IRB, the Investigator and/or Indivior, the amendment to the protocol substantially changes the study design and/or increases the potential risk to the subject and/or has an impact on the subject's involvement as a study subject, the currently approved written ICF will require similar modification. In such cases, informed consent will be renewed for subjects enrolled in the study before continued participation, based on IRB determination.

# **18 STUDY REPORTS AND PUBLICATIONS**

A CSR will be prepared following completion of the study. An Investigator signatory may be identified for the approval of the report if required by applicable regulatory requirements.

The study data will be owned by Indivior. Publication of any and all data will be at the discretion of Indivior. The Investigator will not disseminate, present or publish any of the study data without the prior written approval from Indivior to do so.

# **19 STUDY TERMINATION**

Both Indivior and the Investigator reserve the right to terminate the study at the Investigator's site at any time. Should this be necessary, Indivior, or a specified designee will inform the appropriate Regulatory Authorities of the termination of the study and the reasons for its termination, and the Investigator will inform the IRB of the same. In terminating the study, Indivior and the Investigator will assure that adequate consideration is given to the protection of the subjects' interests.

# 20 CONFIDENTIALITY

All subject-identifying documentation generated in this study is confidential and may not be disclosed to any persons not directly concerned with the study without written permission from the subject. However, authorized regulatory officials and Indivior personnel (or their representatives) will be allowed full access to inspect and copy the records. All subject bodily fluids and/or other materials collected shall be used solely in accordance with this protocol and the ICF signed by the subject, unless otherwise agreed to in writing by Indivior.

Each subject will be identified by an assigned subject number when reporting study information to any entity outside of the study center. During the blinded portion of the study, if use of the subject number could be unblinding, false or 'dummy' subject identifiers may be used. Data containing subject identification will not be removed from the study center without first redacting subject identifiers.

#### 22 APPENDICES

#### 22.1 APPENDIX 1 – Schedule of Events Part I

Evaluation								
	Screening Days		Follow-up					
	-28 to -1	Day -112	Day 1	Day 2	Day 3	Day 4	Day 11/EOS  /ET	
Informed Consent	X						8791	
Inclusion/Exclusion Criteria	X	X						
Randomization		Х						
Demographics (Includes height, weight and BMI)	x							
Medical History	Х		0					
Physical Examination 	X	Х	0	X		X	Х	
Urine Drug Screen	X	X						
Alcohol test	Х	X 						
Serum Pregnancy Test	Х							
Urine Pregnancy Test		Х					Х	
Urinalysis	Х	Х		X				
FSH test (for post-menopausal women only)	х							
Clinical Laboratory Assessments (Chemistry and Hematology)	х	X		X		X	Х	
Serology (HIV, Hepatitis B and C)	Х							
Coagulation Panel (PT/INR)	Х							
Vital Signs 	Х	Х	$X^2$	X		Х	X	
12-Lead Electrocardiogram 	X 	Х	$X^4$	X		Х	X	
26 Hour Holter Monitoring 			Х					

Confidential

Indivior 10 December 2020

INDV-2000	
Clinical Study Protocol: INDV-2000-101	

Indivior 10 December 2020

Evaluation							
	Screening Days		Follow-up				
	-28 to -1	Day -1 	Day 1	Day 2	Day 3	Day 4	Day 11/EOS  /ET
PK Sampling 			X 	Х	X	Х	
Drug Administration 			Х				
AE Assessment		X	Х	X	X	X	Х
Concomitant Medication Assessment	X	X	Х	X	X	Х	Х
Admission to Clinical Unit		X					
Discharge from Clinical Unit						Х	

INDV-2000	
Clinical Study	Protocol: INDV-2000-101

Indivior 10 December 2020

Evaluation						1074134		ALC 1. 1	58 1552/1002			
		Period 1 - Dosing Under Fasting Condition				dition	Period 2 -	Dosing a	fter High-	and the second second second	ent Meal atient	Follow-up
	Screening Days -28 to -1	In clinical unit			Outpatient visits		In clinical unit			visits		
		Day -111	Day 1	Day 2	Day 3	Day 4	Day -1 	Day 1	Day 2	Day 3	Day 4	Day 10/EOS/ET 
Informed Consent	X											
Inclusion/Exclusion Criteria	X	x										
Demographics (Includes height, weight and BMI)	X											
Medical History	X											
Physical Examination 	Х	X		X			X		X			X
Urine Drug Screen	Х	X					X					
Alcohol test	X	X 					X 					
Urinalysis	Х	Х		Х			Х		Х			
Clinical Laboratory Assessments (Chemistry and Hematology)	x	x		x		x	x		x		x	х
Serology (HIV, Hepatitis B and C)	X											
Coagulation Panel (PT/INR)	х											
Vital Signs 	Х	X	X 	X		X	X	X	Х		Х	X
12-Lead Electrocardiogram 	X 	x	X 	x			x	X 	x		-	х
26 Hour Holter Monitoring 			X					X				
PK Sampling 			X 	X	X	X		X 	X	X	X	

#### 22.2 APPENDIX 2 – Schedule of Events Part II

Confidential

Page 71 of 89
INDV-2000	
Clinical Study	Protocol: INDV-2000-101

Indivior 10 December 2020

Evaluation												
			riod 1 - Dosing Under Fasting Condition				Period 2 -	Dosing a	fter High-	Fat Conto	ent Meal	Follow-up
		In	clinical un	it	Outpati	ent visits	Ind	linical un	it		atient sits	
	Screening Days -28 to -1	Day -1 	Day 1	Day 2	Day 3	Day 4	Day -1 	Day 1	Day 2	Day 3	Day 4	Day 10/EOS/ET 
Standard High-Fat Breakfast 								x				7
Drug Administration			X					X 				
AE Assessment		X	X	X	X	X	X	X	X	X	X	X
Concomitant Medication Assessment	x	x	x	x	x	x	x	x	x	x	x	х
Admission to Clinical Unit		x					x					
Discharge from Clinical Unit				X7					X7			

Confidential

Page 72 of 89

INDV-2000 Clinical Study Protocol: INDV-2000-101 Indivior 10 December 2020

# 22.3 APPENDIX 3 – Liver Safety

The following should occur if a subject meets any of the liver chemistry stopping criteria as outlined in Section 6.4 of the protocol:

- Subject should immediately be withdrawn from treatment. Do not re-challenge with study treatment.
- Notify the Indivior Medical Monitor or specified designee within 24 hours of learning of the abnormality.
- Completed the "Safety Follow-up Procedures" listed below.
- Upon completion of the safety follow-up, the subject must be withdrawn from the study unless further follow-up is required.

## Subjects with ALT ≥3x ULN and bilirubin ≥2x ULN (>35% direct); or ALT ≥3x ULN and INR >1.5:

**This event is an SAE** and should be reported using the SAE Reporting Form (Section 11). Serum bilirubin fractionation should be performed, if testing is available. If fractionation is unavailable, urinary bilirubin is to be measured via dipstick (a measurement of direct bilirubin, which would suggest liver injury).

Make every reasonable attempt to have the subject return to the clinic within 24 hours for repeat liver chemistries, additional testing and close monitoring (with specialist or hepatology consultation recommended).

Monitor the subject twice weekly until liver chemistries (ALT, AST, alkaline phosphatase, bilirubin) resolve, stabilize or return to within baseline values.

#### Subjects with ALT $\geq$ 5x ULN or ALT $\geq$ 3x ULN who have hepatitis symptoms or rash, cannot be monitored for 4 weeks or have elevations that persist $\geq$ 4 weeks:

- Make every reasonable attempt to have the subject return to the clinic within 24-72 hours for repeat liver chemistries and additional testing.
- Monitor subject weekly until liver chemistries (ALT, AST, alkaline phosphatase, bilirubin) resolve, stabilize or return to within baseline values.

### Subjects with ALT ≥3x ULN and <5x ULN and bilirubin <2x ULN, who do not exhibit hepatitis symptoms or rash:

Confidential

- Contact the Indivior Medical Monitor within 24 hours of learning of the abnormality to discuss subject safety.
- Subject may continue study treatment, if liver chemistries (ALT, AST, alkaline phosphatase, bilirubin) can be monitored weekly for up to 4 weeks.
- If the subject later meets the liver chemistry stopping criteria (outlined in Section 6.5 of the protocol), immediately withdraw study treatment, perform additional testing and continue safety follow-up until liver chemistries resolve, stabilize or return to baseline values.
- After 4 weeks of monitoring, if ALT <3x ULN and bilirubin <2x ULN, subject must be monitored twice monthly until liver chemistries normalize or return to within baseline values.

### Additional follow-up procedures for subjects who meet any of the stopping criteria:

- Viral hepatitis serology including:
  - Hepatitis A Immunoglobulin M (IgM) antibody,
  - HBsAg and Hepatitis B Core Antibody (IgM),
  - Hepatitis C RNA,
  - Cytomegalovirus IgM antibody,
  - Epstein-Barr viral capsid antigen IgM antibody (or if unavailable, obtain heterophile antibody or monospot testing), and
  - Hepatitis E IgM antibody.
  - Blood sample for PK analysis, obtained within 48 hours of last dose.
  - Serum creatine phosphokinase and lactate dehydrogenase.
  - Fractionate bilirubin, if total bilirubin  $\geq 2x$  ULN.
  - Assess eosinophilia.
  - Record the appearance or worsening of clinical symptoms of hepatitis (fatigue, nausea, vomiting, right upper quadrant pain or tenderness, fever, rash or eosinophilia) as relevant on the AE eCRF.
  - Record use of concomitant medications, acetaminophen, herbal remedies, other over-the-counter medications or putative hepatotoxins on the Concomitant Medications eCRF.

- Record alcohol use in the eCRF.
- In addition, the following are required for subjects with ALT ≥3x ULN and bilirubin ≥2x ULN (<35% direct) but optional for other abnormal liver chemistries:
  - Anti-nuclear antibody, anti-smooth muscle antibody, Type 1 anti-liver kidney microsomal antibodies and quantitative total immunoglobulin G (IgG or gamma globulins).
  - Serum acetaminophen adduct High-Performance Liquid Chromatography (HPLC) assay (quantifies potential acetaminophen contribution to livery injury in subjects with definite or likely acetaminophen use in the preceding week [
  - James 2009]).
  - Liver imaging (ultrasound, MRI, or CT) to evaluate liver disease. Data should be entered into the eCRF, if these tests are performed.

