### Table 1 List of Laboratory Tests

Confidential

Microscopic examination of sediment a	Potassium
Nitrite	Sodium
Occult blood	Total bilirubin
pH	Direct bilirubin
Protein	Total cholesterol
Specific gravity	Total protein
Urobilinogen	Triglycerides
Hormone Panel:	Urine Drug Screen (UDS):
Follicle Stimulating Hormone	Opioids
	Cocaine
Pregnancy:	Amphetamines
Serum hCG	Cannabinoids
	Barbiturates
Screening Only:	Benzodiazepines
Hemoglobin A1c	Methamphetamine
Hepatitis B surface Antigen	Phencyclidine
Hepatitis C Antibody	Ethanol
HIV-1 and -2 antibodies	
Prothombin Time (PT) with INR	
PTT	

Anti-HIV = human immunodeficiency virus antibodies; hCG = human chorionic gonadotropin; INR = international normalized ratio; PT = prothrombin time; and PTT = partial thromboplastin time.

a Microscopic examination of sediment will be performed only if the results of the urinalysis evaluation are positive (microscopic examination may include but is not limited to White Blood Cell count, Red Blood Cell count, casts and crystals).

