### 9.6.1 Permitted Concomitant Therapies

The Investigator may prescribe concomitant medications or treatments for pain (acetaminophen up to 2000 mg per 24 hr, ibuprofen up to 600 mg per 24 hr administered orally) or nausea (promethazine 25 mg oral or suppository) as deemed necessary for the comfort of the subject. For oral therapies, please withhold dosing for at least 2 hr before or 1 hr after administration of IMP.

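### Protocol Appendix 3 requires three extended liver tests only when direct bilirubin is below 35%, which leaves them optional for its own bilirubin-based SAE group (above 35% direct)

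*Protocol*

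**What the plan says.** Protocol Section 22.3 (Appendix 3, Liver Safety) sorts subjects with raised liver chemistries into groups and then lists additional follow-up for anyone who meets a stopping criterion.

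The most serious group is headed "Subjects with ALT ≥3x ULN and bilirubin ≥2x ULN (>35% direct); or ALT ≥3x ULN and" INR above 1.5. Events in this group are SAEs. If fractionation is unavailable, the text asks for a urine dipstick, which it explains as "a measurement of direct bilirubin, which would suggest liver injury". Every reasonable attempt is to be made to bring the subject back within 24 hours for repeat chemistries and further testing, with specialist or hepatology consultation recommended. The instruction continues: "Monitor the subject twice weekly until liver chemistries" resolve, stabilise or return to baseline.

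The additional follow-up list ends with three items under a separate condition: "the following are required for subjects with ALT ≥3x ULN and bilirubin ≥2x ULN (<35% direct) but optional for other abnormal liver chemistries". They are the autoantibody and total IgG panel, the acetaminophen-adduct assay and liver imaging. The adduct assay is described as measuring acetaminophen's contribution "in subjects with definite or likely acetaminophen use in the preceding week".

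Section 11 makes potential Hy's Law cases SAEs, using ALT ≥3x ULN with total bilirubin ≥2x ULN (or a raised INR) and no direct fraction. It sends them to Appendix 3 for management.

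**The concern.** The two conditions in Appendix 3 use the same ALT and bilirubin limits and the same 35% cut, but with opposite signs. The appendix treats a high direct fraction as the mark of liver injury and gives that group its most intensive monitoring. It then reserves the mandatory extended tests for the low direct fraction. No text explains why that subset alone should have them, and a fraction below 35% defines no group anywhere else in the protocol.

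The stated purposes of two of the items also fit the group above 35%: the assay helps to attribute liver injury, and imaging evaluates liver disease. If a suspected case of liver injury arose in this first-in-human study, a site following the text literally could omit tests that help to establish its cause and still comply with the protocol.

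**Working it through.** The plan gives no figure to reproduce. The check is to apply each rule to a subject who has met a stopping criterion and has ALT ≥3x ULN and bilirubin ≥2x ULN, with INR not above 1.5, and to vary only the direct fraction.

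| Direct fraction | SAE under Section 11 | In the bilirubin limb of the Appendix 3 SAE group | Three items as written | If the sign is flipped | If the qualifier is deleted |
|---|---|---|---|---|---|
| above 35% | yes | yes | optional | required | required |
| below 35% | yes | no | required | optional | required |
| exactly 35% | yes | no | optional | optional | required |

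1. Above 35% and below 35% cannot both be true. Every subject in the bilirubin limb of the SAE group therefore fails the condition for the three items and falls among the other abnormal liver chemistries, for which they are optional.
2. Nothing else restores the requirement. The SAE-group text asks for additional testing without naming these tests. Section 11.1 has the investigator attempt a diagnosis of an SAE but mandates no test. Section 11 only refers back to Appendix 3.
3. What remains mandatory: eight entries in the follow-up list carry no direct-fraction condition. They are viral serology, a PK sample, creatine phosphokinase and lactate dehydrogenase, bilirubin fractionation (triggered by total bilirubin ≥2x ULN, so it applies here), eosinophilia, symptoms, concomitant medication and alcohol use.
4. What is lost: the mandatory status of up to three items. If the description of the adduct assay is read as limiting it to recent acetaminophen users, the loss is three items for those subjects and two for the rest. Recent use is possible, because Section 9.6.1 permits "acetaminophen up to 2000 mg per 24 hr".
5. The condition can be applied in practice. Table 1 includes "Direct bilirubin", and the row "Clinical Laboratory Assessments (Chemistry and Hematology)" in the schedules places draws after the first dose on Days 2, 4 and 11 in Part I (3 draws). In Part II they fall on Days 2 and 4 of Period 1, Days -1, 2 and 4 of Period 2, and Day 10 (2 + 3 + 1 = 6 draws). These are occasions on which the fraction is available, not expected cases.

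**The case against.** The strongest reply is that no inconsistency has been shown. One text sets SAE reporting and monitoring, the other allocates extra tests, and nothing says that their groups must coincide. That stands: both rules can be obeyed at once, and a reader who inferred a logical contradiction would go beyond the text. The intended sign is also an inference. It rests on the dipstick remark, the stated purpose of the tests, and the lack of any reason for the low-fraction subset.

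A reader might also infer that the group above 35% direct gets the weaker follow-up overall. The documents do not support that; it is true only within the additional follow-up list. The SAE-group text gives these subjects the closest monitoring in the appendix. By contrast, an asymptomatic subject with ALT from 3x to below 5x ULN, bilirubin ≥2x ULN, a fraction below 35% and INR not above 1.5 fits none of the monitoring groups on those values alone.

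Expressing the loss as a share of listed items is fragile too. Counting entries gives 3 of 8 + 3 = 11. Counting the six viral serologies separately gives 3 of 7 + 6 + 3 = 16. Neither ratio measures risk.

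Finally, the point turns on one character in text read by a program from PDF, and the liver stopping criteria of Section 6.4 are not visible in the public version. A misread sign is unlikely but cannot be excluded. The hidden criteria decide who reaches the list, not which sign applies once there.

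**Conclusion.** The point holds as a probable sign error in an operative safety rule. As printed, the autoantibody and IgG panel, the adduct assay and imaging are optional for every subject in Appendix 3's bilirubin-based SAE group, and required only for subjects below 35% direct.

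Its weight is low. Investigators may still order the tests. The documents give no expected frequency, and cases should be rare after single doses in healthy volunteers. The condition does not decide whether an event is an SAE, and no endpoint, analysis population or planned analysis depends on it.

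The conclusion assumes that both signs are printed as supplied. It does not extend to the INR limb of the SAE group, where the requirement depends on whether the bilirubin condition is also met.

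**What to change.** In the last item of the additional follow-up list in Protocol Appendix 3, delete the direct-fraction qualifier so that the three tests are required for ALT ≥3x ULN and total bilirubin ≥2x ULN. This matches the bilirubin criterion in Section 11, covers fractions on both sides of 35% and at 35% itself, and works whichever sign was intended.

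Do not simply turn the sign round. That would cover the group above 35% but make the tests optional for subjects below 35%, who are also SAEs under Section 11.

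The cost is one condition in one sentence at the next amendment, with no new scheduled visits and no new kinds of test. The downside is that up to three tests already specified in the protocol become mandatory in a rare case.

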# 22.4 APPENDIX 4 – Pharmacokinetic Sampling Windows Part I

Day	Timepoint	Assessment	Window	
Day 1	pre-dose			
Day 1	0.5 hr post-dose			
Day 1	1 hr post-dose			
Day 1	2 hr post-dose			
Day 1	3 hr post-dose			
Day 1	4 hr post-dose			
Day 1	6 hr post-dose			
Day 1	8 hr post-dose			
Day 1	12 hr post-dose			
Day 2	24 hr post-dose			
Day 3	48 hr post-dose			
Day 4	72 hr post-dose			

